5.5 Duration of Therapy

If at any time the constraints of this protocol are considered to be detrimental to the patient's health and/or the patient no longer wishes to continue protocol therapy, the protocol therapy should be discontinued and the reason(s) for discontinuation documented in the case report forms.

In the absence of treatment delays due to adverse events, treatment may continue indefinitely or until one of the following criteria applies:

- Documented and confirmed disease progression
- Death
- Adverse event(s) that, in the judgment of the investigator, may cause severe or permanent harm or which rule out continuation of study drug
- General or specific changes in the patient's condition render the patient unable to receive further treatment in the judgment of the investigator
- Suspected pregnancy
- Serious non-compliance with the study protocol
- Lost to follow-up
- Patient withdraws consent
- Investigator removes the patient from study
- The Siteman Cancer Center decides to close the study

Patients who prematurely discontinue treatment for any reason will be followed as indicated in the study calendar.

5.6 Duration of Follow-up

After coming off treatment, patients will be followed for 30 days to collect adverse events. Patients removed from study for unacceptable adverse events will be followed until resolution or stabilization of the adverse event.

6.0 DOSE DELAYS/DOSE MODIFICATIONS

6.1 Hormone Therapy Dose Modifications

No dose adjustments are permitted for fulvestrant or letrozole, but interruptions are allowed at the discretion of the treating physician. Hormonal therapy should continue while holding palbociclib due to palbociclib related AEs.

6.2 Ovarian Suppression Dose Modifications

No dose adjustments are permitted for goserelin.

6.3 Dose Modifications for Palbociclib

Patients will be monitored for toxicity and the dose of palbociclib may be adjusted as indicated in the dose modification table below.

Dose Level	Palbociclib 5 Days On / 2 Days Off
1 (starting dose)	125 mg/day
-1	100 mg/day
-2	75 mg/day
Note that palbociclib dose reduction below 75 mg/day is not allowed	

Dose reduction by 1 and, if needed, 2 dose levels will be allowed depending on the type and severity of toxicity encountered. Patients requiring more than 2 dose reductions will be discontinued from the study.

Recommended dose reductions for palbociclib are detailed in the table below. Doses may be held as needed for toxicity resolution during a cycle. Doses omitted for toxicity are not replaced or restored within the same cycle (meaning that the cycle remains 28 days regardless of the number of doses of taken).

Treatment with palbociclib should be permanently discontinued if toxicity has not recovered to grade ≤ 2 within two weeks.

Palbociclib Dose Modifications Based on Worst Treatment-Related Toxicity in the Previous Cycle

Worst Toxicity During Previous Cycle	New Dose Level
Grade 4 neutropenia	Decrease by one dose level
Grade 4 thrombocytopenia	Decrease by one dose level
Grade 3 neutropenia associated with a documented infection or fever ≥ 38.5 °C	Decrease by one dose level
Grade ≥ 3 non-hematologic toxicity (includes nausea, vomiting, and diarrhea only if persisting despite maximal medical treatment)	Decrease by one dose level
Delay by > 1 week in receiving the next scheduled dose due to persisting treatment-related toxicities	If recovery occurs within 2 weeks, continue and decrease by one dose level
Inability to deliver at least 80% of the planned dose of PD 0332991 due to adverse events possibly related to study treatment	Decrease by one dose level

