1.3 Study Rationale

The current dose modification guidelines for palbociclib are as follows:

CTCAE* grade	Dose modifications
Grade 1 or 2	No adjustment required
Grade 3	No dose adjustment is required. Consider repeating complete blood count monitoring one week later. Withhold initiation of next cycle until recovery to Grade ≤ 2
Grade 3 ANC (<1000 to 500/mm ³) + Fever ≥ 38.5 C and/or infection	Withhold Palbociclib and initiation of next cycle until recovery to Grade ≤ 2 (≥ 1000 /mm ³). Resume at next lower dose
Grade 4	Withhold Palbociclib and initiation of next cycle until recovery to Grade ≤ 2 . Resume at next lower dose

*Common terminology criteria for adverse events

We propose to conduct a study to test an alternative dosing schedule of palbociclib. With the current three-week on and one week off schedule, a significant number of patients develop grade 3 or higher degree of neutropenia and require dose reduction and sometimes discontinuation. This potentially compromises the efficacy of the drug. In addition, as the half-life of palbociclib is 27 hours, 1 week break with the standard 3 weeks on and 1 week off dosing schedule could potentially lead to recovery of Rb phosphorylation during the off week. Hence, we propose a 5 days on and 2 days off schedule each week without any weeks off drug. Although the cumulative doses each 28-day cycle is roughly the same with this schedule compared to conventional dosing, the bone marrow is not exposed to the drug continuously for 21 days and rather gets frequent breaks from therapy. We hypothesize that the 5 days on and 2 days off schedule is more tolerable with less frequent high grade neutropenia and dose interruption/reduction. In addition, this schedule also provides for a more continuous drug delivery to the patient since there is not a week's break in therapy, which could ultimately prove to be more efficacious.

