6.4 Re-Treatment Criteria

A new cycle of treatment with palbociclib may begin only if:

- ANC \geq 1,000/mcL.
- Platelet count \geq 50,000/mcL.
- Non-hematologic toxicities have returned to baseline or Grade \leq 1 severity (or, at the investigator's discretion, Grade \leq 2 if not considered a safety risk for the patient).

Criteria for dose interruption within cycle:

- ANC $<$ 500/mcL.
- Platelet count $<$ 50,000/mcL.

Re-treatment within the cycle may only be started when ANC \geq 500/mcL and platelet count \geq 50,000/mcL.

Doses omitted for toxicity within a cycle are not replaced or restored within the same cycle (meaning that the cycle remains 28 days regardless of the number of doses of taken).

If these conditions are not met, hormone therapy may be continued but treatment with palbociclib must be delayed by one week. If, after a one-week delay, all toxicities have recovered within the limits described above, treatment with palbociclib can be resumed.

If the patient has not recovered after 2 weeks despite dose reduction to the lowest dose level, treatment with palbociclib will be permanently discontinued.

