10.0 STUDY CALENDAR

Screening/baseline evaluations are to be conducted within 2 weeks prior to start of protocol therapy. Scans and x-rays must be done no more than 4 weeks prior to the start of the protocol therapy. There is a +/-3 day window around each study visit.

	Screening	Baseline	Day 1 of each cycle ⁸	C1D15	C2D1	C2D15	End of every 2 nd or 3 rd cycle ⁸	Time of progression	30 day f/u
Informed consent	X								
H&P, ECOG PS	X		X		X			X	
CBC w/diff	X		X	X	X	X			
CMP	X		X		X				
β-hCG ¹	X								
Imaging	X						X	X	
Palbociclib			Given on a 5 days on / 2 days off schedule for each 28-day cycle						
Fulvestrant ³			X	X	X				
Letrozole ³			Daily						
Goserelin ⁴			X		X				
Medication diary			Daily, to be returned at the end of each cycle						
AE assessment			X -----X						
Archival Tissue		X ⁷							
Research biopsy (optional)		X						X	
Blood for serum		X		X ⁵	X ⁵		X ^{2,5}	X	
Blood for plasma		X		X ⁵	X ⁵		X ^{2,5}	X	
Blood for cfDNA		X		X ⁵	X ⁵		X ^{2,5}	X	
Blood for germline DNA		X							
Blood for circulating tumor cells		X			X		X ⁶	X	

1. Women of childbearing potential only
2. Beginning with the end of Cycle 2 but to coincide with imaging studies
3. Either fulvestrant OR letrozole will be given (MD decision)
4. Goserelin will be given to premenopausal women only
5. Instruct patient take palbociclib/hormonal therapy after blood draw, meaning blood draw needs to happen prior to the day's treatment.
6. Post 2 or 3 months after start of therapy (to coincide with ONLY the 1st imaging assessment of tumor response)
7. Archival tissue should include both primary and metastatic tissue
8. Labs and office visits could be reduced in frequency to q2-3 cycles to coincide with tumor imaging studies in patients on stable doses of palbociclib for at least 6 consecutive cycle

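### Sections 6.3 and 6.4 give different rules for permanently stopping palbociclib in a patient above 75 mg/day who is unrecovered at two weeks, and they define recovery differently

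*Combined protocol and SAP*

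**What the plan says.** Both rules are in section 6 of the protocol.

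- **6.3, stop rule:** "Treatment with palbociclib should be permanently discontinued if toxicity has not recovered to grade ≤ 2 within two weeks". No dose level is mentioned.
- **6.3, dose-modification table, row for a delay of more than one week:** "If recovery occurs within 2 weeks, continue and decrease by one dose level". The row does not say what follows if recovery takes longer.
- **6.4, delay step:** when the re-treatment conditions are not met, palbociclib is put back one week. Then: "If, after a one-week delay, all toxicities have recovered within the limits described above, treatment with palbociclib can be resumed".
- **6.4, stop rule:** "If the patient has not recovered after 2 weeks despite dose reduction to the lowest dose level, treatment with palbociclib will be permanently discontinued".
- **6.4, recovery limits:** a new cycle needs ANC of at least 1,000/mcL and platelets of at least 50,000/mcL. For other toxicities the text begins "Non-hematologic toxicities have returned to baseline or Grade" and sets the limit at grade 1, or grade 2 at the investigator's discretion. Re-treatment within a cycle needs only ANC of at least 500/mcL and platelets of at least 50,000/mcL.

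**The concern.** A permanent stop is among the most consequential instructions in a treatment protocol, so two sites should reach the same decision for the same patient. Here a site working from 6.3 would end palbociclib for a patient at the starting dose who is unrecovered at two weeks. A site working from 6.4 would find that its stop condition is not met, and could reasonably conclude that she may resume if she recovers later.

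Two things are at stake. The first is which patients lose the study drug permanently. The second is secondary objective 2, the rate of palbociclib dose reduction, interruption or discontinuation (section 2.2). Its discontinuation part would then reflect partly which section a site followed, and not only how well the schedule is tolerated.

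**Working it through.** No statistical figure in the plan depends on this rule, so the check is mainly a comparison of the texts.

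**1. Dose levels.** Section 6.3 lists 125, 100 and 75 mg/day and allows nothing below 75. The lowest dose level in 6.4 is therefore 75 mg/day.

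**2. The two rules by dose level**, for a patient due to start a new cycle and unrecovered at two weeks:

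| Patient | 6.3 | 6.4 |
|---|---|---|
| 125 mg/day, toxicity above grade 2 | permanent stop | stop condition not met; no next step |
| 100 mg/day, toxicity above grade 2 | permanent stop | stop condition not met; no next step |
| 75 mg/day, toxicity above grade 2 | permanent stop | permanent stop |
| 75 mg/day, grade 2 non-hematologic toxicity that the investigator does not accept | recovered; no stop | not recovered; permanent stop |

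For toxicity above grade 2 the rules diverge at 2 of the 3 dose levels, including the starting dose.

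**3. Does other text settle it?**
- The 6.4 resume sentence covers recovery after a one-week delay, and the 6.3 delay row covers recovery within two weeks. Neither covers later recovery.
- Section 5.5 lists neither rule, and its continuation clause is conditional: "In the absence of treatment delays due to adverse events, treatment may continue indefinitely or until one of the following criteria applies". It does include adverse events that the investigator judges to preclude further drug, but that is discretionary and does not choose between the rules.
- Section 6.3.1 deals only with QTc and gives no two-week limit.
- The table in section 1.3 describes current guidelines as background and contains no two-week rule.

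**4. Recovery limits.** Section 1.3 equates grade ≤ 2 for ANC with at least 1,000/mm³ ("Withhold Palbociclib and initiation of next cycle until recovery to Grade ≤ 2 (≥ 1000 /mm"³) and places 500 to <1,000 in grade 3.
- ANC at the start of a cycle: 6.3 (grade ≤ 2) and 6.4 (at least 1,000/mcL) agree.
- ANC within a cycle: 6.4 allows re-treatment from 500/mcL. A patient at 500 to <1,000 may be dosed under 6.4 while still unrecovered in the sense of 6.3.
- Non-hematologic toxicity: 6.3 uses grade ≤ 2. 6.4 uses baseline or grade ≤ 1, with grade ≤ 2 only at discretion.

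**5. Start of the two weeks.** Neither stop sentence gives a day zero. The 6.3 delay row counts from a late scheduled dose, and 6.4 moves from a one-week delay to two weeks. Both suggest the start of the dosing delay. However, the 6.3 stop sentence speaks of toxicity and not of delay, and 6.3 also allows doses to be held within a cycle, so the start should be stated.

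**6. Size.** Planned enrollment is 47 (section 15.2). Assuming all 47 form the denominator, each patient handled differently moves the discontinuation rate by 1/47 = 2.1 percentage points, and k patients move it by k × 2.1. The documents do not give k.

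For rough scale only, section 1.2 reports adverse-event discontinuation on palbociclib of 2.6%, 9.7% and 13% in three earlier trials on other schedules. Applied to 47 patients, these give 0.026 × 47 = 1.2, 0.097 × 47 = 4.6 and 0.13 × 47 = 6.1 patients. If totals here were similar, one patient could be a visible share of the count. These figures do not estimate k, which may be zero.

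**The case against.** **The sections can both be obeyed.** Section 6.4 says when palbociclib will be stopped. It does not say that this is the only circumstance, and nothing in it expressly lets a patient above 75 mg/day resume after two weeks. A site that stops her under 6.3 breaches nothing in 6.4. Section 6.3 also says should, where 6.4 says will. This stands, and it limits the point to a conflict by implication. A reader might infer a flat contradiction, with 6.4 authorizing later resumption, but the text does not go that far.

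**The dose condition in 6.4 might have its own purpose.** If 6.3 applied at every level, the condition would seem to do nothing. The last row of the table shows that this is not quite so: the stricter non-hematologic limit in 6.4 can stop a patient at 75 mg/day whom 6.3 would not. This partly stands. The redundancy argument is strongest for ANC at the start of a cycle, where the recovery limits coincide.

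**Different thresholds can serve different decisions.** One limit governs stopping and the other governs starting a cycle, so a difference is not in itself an error. That is fair, but 6.4 also contains a stop rule that appears to use its own limits, so two recovery definitions bear on the same decision.

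**The clock is reasonably clear.** A reader might start it at the first grade 3 count. A low ANC on Cycle 1 Day 15 would then lead to a stop on Day 15 + 14 = 29, against Day 29 + 14 = 43 if the clock starts at a delay of Cycle 2 Day 1. The documents give little support for the Day 29 reading. Both sections point to the dosing delay, an uncomplicated grade 3 count requires no within-cycle hold under 6.4, and the study calendar schedules no blood count between those two visits that would show continuous non-recovery. What stands is that the start is not explicitly defined.

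**Conclusion.** The point holds as an inconsistency by implication between two stated stopping rules. For patients at 125 or 100 mg/day with toxicity still above grade 2 at two weeks, 6.3 calls for a permanent stop, while 6.4 neither stops them nor says what to do next. No other section resolves this. The differing recovery limits and the undefined start of the two weeks add to the uncertainty.

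The consequence is for patient management and, in a small way, for secondary objective 2: 2.1 points on the discontinuation component per affected patient, assuming a denominator of 47. If objective 2 is reported as a single composite rate, the change would be smaller still, because a delayed patient is probably already counted as interrupted.

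Two stronger readings should not be drawn. A reader might infer that no dosing is allowed while a patient is unrecovered. That is true only for starting a new cycle, since within a cycle 6.4 allows dosing at a grade 3 ANC. A reader might also infer that the primary result is at risk. The stop rule does not enter the primary endpoint definition, the decision cut-off, alpha or power.

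The sponsor should correct this, but it does not threaten the trial's main conclusion.

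**What to change.** Reconcile sections 6.3 and 6.4 into one rule for permanent discontinuation and resumption of palbociclib. The rule should state:

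- the dose levels to which it applies;
- the event from which the two weeks are counted;
- the definition of recovery, separately for a new cycle and within a cycle if these are meant to differ, and for ANC, platelets and non-hematologic toxicity;
- what happens to a patient who recovers only after the two weeks.

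Which rule to adopt is the sponsor's clinical decision, and this review takes no position on it. The cost is amendment wording and notification of the sites, with no extra patients, visits or procedures.

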6.3.1 Dose Adjustments Due to QTc Prolongation

Any patients who develops new grade 2 or greater ECG QT corrected interval prolonged at any time during the study will need to have the ECG repeated immediately for confirmation.

Grade 2: no adjustments; continue at same dose level

Grade 3 (reversible cause identified and corrected): withhold treatment until QTc \leq 470 msec, then resume treatment at the same dose level

Grade 3 (no reversible cause identified): withhold treatment until QTc \leq 470 msec, then decrease palbociclib by one dose level

Grade 4: permanently discontinue palbociclib

6.4 Re-Treatment Criteria

A new cycle of treatment with palbociclib may begin only if:

- ANC \geq 1,000/mcL.
- Platelet count \geq 50,000/mcL.
- Non-hematologic toxicities have returned to baseline or Grade \leq 1 severity (or, at the investigator's discretion, Grade \leq 2 if not considered a safety risk for the patient).

Criteria for dose interruption within cycle:

- ANC $<$ 500/mcL.
- Platelet count $<$ 50,000/mcL.

Re-treatment within the cycle may only be started when ANC \geq 500/mcL and platelet count \geq 50,000/mcL.

Doses omitted for toxicity within a cycle are not replaced or restored within the same cycle (meaning that the cycle remains 28 days regardless of the number of doses of taken).

If these conditions are not met, hormone therapy may be continued but treatment with palbociclib must be delayed by one week. If, after a one-week delay, all toxicities have recovered within the limits described above, treatment with palbociclib can be resumed.

If the patient has not recovered after 2 weeks despite dose reduction to the lowest dose level, treatment with palbociclib will be permanently discontinued.

7.0 REGULATORY AND REPORTING REQUIREMENTS

The entities providing oversight of safety and compliance with the protocol require reporting as outlined below.

The Washington University Human Research Protection Office (HRPO) requires that all events meeting the definition of unanticipated problem or serious noncompliance be reported as outlined in Section 7.2.

Pfizer requires that all serious adverse drug experiences (defined as the events described in Sections 7.1.2, 7.1.3, and 7.1.4) be reported as outlined in Section 7.6.

7.1 Definitions

7.1.1 Adverse Events (AEs)

Definition: any unfavorable medical occurrence in a human subject including any abnormal sign, symptom, or disease.

Grading: the descriptions and grading scales found in the revised NCI Common Terminology Criteria for Adverse Events (CTCAE) version 4.0 will be utilized for all toxicity reporting. A copy of the CTCAE version 4.0 can be downloaded from the CTEP website.

Attribution (relatedness), Expectedness, and Seriousness: the definitions for the terms listed that should be used are those provided by the Department of Health and Human Services' Office for Human Research Protections (OHRP). A copy of this guidance can be found on OHRP's website:

<http://www.hhs.gov/ohrp/policy/advevntguid.html>

7.1.2 Serious Adverse Event (SAE)

Definition: any adverse drug experience occurring at any dose that results in any of the following outcomes:

- Death
- A life-threatening adverse drug experience
- Inpatient hospitalization or prolongation of existing hospitalization
- A persistent or significant disability/incapacity (i.e., a substantial disruption of a person's ability to conduct normal life functions)
- A congenital anomaly/birth defect
- Any other experience which, based upon appropriate medical judgment, may jeopardize the subject and may require medical or surgical intervention to prevent one of the outcomes listed above

7.1.3 Unexpected Adverse Experience

Definition: any adverse drug experience, the specificity or severity of which is not consistent with the current investigator brochure (or risk information, if an IB is not required or available).

7.1.4 Life-Threatening Adverse Experience

Definition: any adverse drug experience that places the subject (in the view of the investigator) at immediate risk of death from the reaction as it occurred, i.e., it does not include a reaction that, had it occurred in a more severe form, might have caused death.

7.1.5 Unanticipated Problems

Definition:

- unexpected (in terms of nature, severity, or frequency) given (a) the research procedures that are described in the protocol-related documents, such as the IRB-approved research protocol and informed consent document; and (b) the characteristics of the subject population being studied;
- related or possibly related to participation in the research (“possibly related” means there is a reasonable possibility that the incident, experience, or outcome may have been caused by the procedures involved in the research); and
- suggests that the research places subjects or others at a greater risk of harm (including physical, psychological, economic, or social harm) than was previously known or recognized.

7.1.6 Noncompliance

Definition: failure to follow any applicable regulation or institutional policies that govern human subjects research or failure to follow the determinations of the IRB. Noncompliance may occur due to lack of knowledge or due to deliberate choice to ignore regulations, institutional policies, or determinations of the IRB.

7.1.7 Serious Noncompliance

Definition: noncompliance that materially increases risks, that results in substantial harm to subjects or others, or that materially compromises the rights or welfare of participants.

7.1.8 Protocol Exceptions

Definition: A planned deviation from the approved protocol that are under the research team's control. Exceptions apply only to a single participant or a singular situation.

Local IRB pre-approval of all protocol exceptions must be obtained prior to the event. For secondary sites, the Washington University PI will issue approval of the exception, but it must also be submitted to the local IRB with documentation of approval forwarded to Washington University. Washington University IRB approval is not required for protocol exceptions occurring at secondary sites.

